1.2 Androgen deprivation therapy and metabolic syndrome

While many new agents have been developed for the treatment of prostate cancer, these focus on treatment in the metastatic, castrate-resistant setting. Patients requiring systemic therapy for prostate cancer continue to be initially treated with traditional gonadotropin hormone analogues, despite advances in therapeutic development. The treatment is very effective with survival results mainly impacted by disease state at initiation. The average time from biochemical recurrence, or prostate specific antigen (PSA) relapse, to development of metastatic disease is approximately 8 years² and survival for patients with metastatic disease on ADT is approximately 30 months. The median time of response for patients with biochemically relapsed disease treated with ADT is 10.8 months³. Thereafter, patients remain on ADT in combination with other therapies for the duration of their anti-cancer therapy, which may be years. Men treated with ADT experience long-term adverse effects such as fatigue, loss of muscle mass (i.e. sarcopenia), loss of bone density, increased adiposity, development of metabolic syndrome, depression, sexual dysfunction and poor quality of life (QOL)⁴⁻¹³. Men treated with ADT had lower levels of self-reported physical function and QOL in comparison to age-matched controls^{8,10,14-17}. These effects are profound for any patients but may be felt to a larger degree in the standard older patient population afflicted with prostate cancer, already dealing with the changes of decreasing functional reserve.

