4. STUDY DESIGN

4.1 Overview of Study Design

This study is a multi-center, open label, randomized, phase II trial of the incidence of metabolic syndrome within 12 months in patients treated with enzalutamide in comparison with androgen deprivation therapy for treatment of advanced prostate cancer. This will include patients with biochemically recurrent disease, metastatic disease, and patients offered ADT as primary therapy if they are not candidates for local therapy. Fifty-six patients will be 1:1 randomized to one of two treatment arms with metastasis as a stratification factor. Patients will be treated for a 12-month period continuously and assessed for the development of metabolic syndrome at 3-month intervals.

Treatment will be administered for a 12-month period. Enzalutamide will be taken orally on each day of the cycle. Androgen deprivation therapy will be administered according to standard of care; however, there will be no intermittent dosing of this treatment. Acceptable forms of ADT must result in castrate levels of testosterone (<50ng/dL), and may include: leuprolide, goserelin, histerelin, triptorelin, degarelix, and surgical castration. Toxicity will be evaluated according to National Cancer Institute Common Terminology Criteria for Adverse Events (NCI CTCAE), Version 4.1 ³⁵. Metabolic syndrome will be diagnosed by assessing a patient's blood pressure, waist circumference, fasting glucose, high density lipoprotein (HDL), and triglyceride level and determined according to the Adult Treatment Panel III criteria ³⁶.

Analysis of bone turnover will include measurement of urinary N-telopeptide and serum bone-specific alkaline phosphatase. A dual-energy x-ray absorptiometry scan (DXA) will also be performed at enrollment, month 3 and EOT. This scan will provide information on bone density changes induced by treatment.

Quality of life questionnaires will be administered at each study visit. Physical function changes will be assessed via the Short Physical Performance Battery; the SPPB incorporates 3 validated portions to assess a patient's balance and mobility. Changes in systemic inflammation will be assessed via circulating hs-CRP levels. Additional collection of complete blood counts and chemistries will provide safety information. This testing will occur in the clinic setting every 3 months as well.

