6.2 Randomization

Randomization will occur using the GraphPad QuickCalcs randomization service.

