6.3.2 Schedule of Events

Screening/Baseline Day -21 - 0

- Informed consent and HIPAA release
- Study eligibility per inclusion/exclusion criteria
- Medical history/baseline conditions
- Physical examination
- Vital signs, including height and weight, waist circumference
- ECOG performance status
- Blood samples for hematology, comprehensive metabolic panel (fasting), lipid profile
- Serum Testosterone
- Serum PSA
- 25-OH Vitamin D
- CT scan and assessment of tumor burden, may use imaging study within 28 days of day 1
- Bone scan, may use imaging study within 28 days of day 1
- Collection of concomitant medications
- Collection of adverse events

Month 1 Day 1

COMIRB/Protocol # 14-0909**Protocol Version:****4.27.2018 PI: [name]**

- Physical examination
- Vital signs, including weight and waist circumference
- ECOG performance status
- Blood samples for CBC, Comprehensive metabolic panel (fasting), PSA, N-telopeptide, bone specific alkaline phosphatase, estradiol, hs-CRP
- Optional tubes of blood for future biomarker testing
- FACT-P, SHIM completed
- DXA scan (+/-14 Days of Day 1 Dosing); note that there must be a 14 day separation of bone scan and a DXA scan
- Short Physical Performance Battery
- Collection of concomitant medications
- Collection of adverse events
- Dosing of medication, or documentation of continued dosing
- Verification of calcium/vitamin D administration

Month 2 Day 1 +/- 5 days

- Physical examination
- Vital signs, including weight and waist circumference
- ECOG performance status
- Blood samples for CBC, Comprehensive metabolic panel (fasting), PSA, testosterone
- Collection of concomitant medications
- Collection of adverse events
- Dosing of medication, or documentation of continued dosing
- Verification of calcium/vitamin D administration

Month 4 Day 1+/- 5 days

- Physical examination
- Vital signs, including weight and waist circumference
- ECOG performance status
- Blood samples for CBC, Comprehensive metabolic panel (fasting), testosterone, PSA, N-telopeptide, bone specific alkaline phosphatase, lipid profile, estradiol, hs-CRP
- Optional tube of blood for future biomarker testing
- FACT-P, SHIM completed
- DXA scan (+/-14 Days of Day 1 Dosing); note that there must be a 14 day separation of bone scan and a DXA scan
- Short Physical Performance Battery
- Collection of concomitant medications
- Collection of adverse events
- Dosing of medication, or documentation of continued dosing

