7.2 Efficacy Evaluations

7.2.1 PSA

Patients will be monitored for clinical efficacy while on study. Serum PSA will be obtained every 3 months. PSA rise is allowable at the discretion of the investigator. However, patients must discontinue treatment if there is evidence of PSA progression as defined by an increase in $\geq 50\%$ from nadir and an absolute increase of at least 2 ng/mL above the nadir, occurring at least 12 weeks after start of therapy that is confirmed by two consecutive increases taken at least 2 weeks apart. The date of first recorded increase will serve as the date of progression.

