7.2.2 Radiographic evaluation

Patients will be removed from study if they have evidence of radiographic disease progression as defined below. Radiographic analysis via CT scan (and/or MRI), and bone scan will occur at baseline, 6 months, and 12 months. For the purposes of this study, investigators should utilize the protocol-specified tumor assessment criteria, defined as assessment of evaluable soft tissue disease sites according to RECIST v1.1, and/or assessment of bone disease according to the PCWG2 criteria. Soft tissue disease will be assessed on CT (or MRI) and defined by RECIST v1.1. Bone disease will be assessed on bone scan and progression will be defined as the development of two or more new bone lesions from baseline confirmed with an additional lesion on bone scan 6 weeks later. New bone lesions noted after the 6-month radiographic assessment do not require a confirmatory bone scan. Increase in intensity of known bone lesions will not constitute progression. The date of progression will be recorded as the date the first scan shows change.

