10.1.1 Endpoint Analysis

Primary endpoint

Metabolic syndrome incidence will be summarized by the proportion of patients with at least 3 of the 5 pre-specified criteria within the first 12 months of therapy.

Secondary endpoint

The secondary endpoints will be presented as follows:

Metabolic syndrome incidence will be summarized by the proportion of patients acquiring with at least 3 of the 5 pre-specified criteria within the first 6 months of therapy.

The change in bone turnover markers from baseline will be assessed for each treatment group. Measurements will be taken at day 1 of each cycle and reported as a continuous variable. A paired t-test will test within an arm as to whether the change from baseline to each time point is significantly different from zero.

The change in bone density, free fat mass, and fat mass will be measured at baseline, 3 months and 12 months and assessed for each treatment group. A paired t-test will test within an arm as to whether the change from baseline to each time point is significantly different from zero.

The change in QOL scores as measured by the FACT-P and SHIM at each visit, will be assessed in each treatment group.

Median time to PSA progression as defined in section 7.2. Time to PSA progression is defined as the time from randomization to the earliest objective evidence of PSA progression as defined per

protocol. If a patient has had a decline in PSA while on study, the PSA progression date is defined as the time from documented PSA nadir to an increase in PSA with confirmation as defined by protocol. Time to radiographic progression is defined as the time from randomization to the earliest objective evidence of radiographic progression as defined per protocol. Patients will be monitored at regular intervals for PSA change and radiographic change. Log rank test will be used to compare the distributions of above variables between the group treated with enzalutamide to the group on standard ADT.

The change in markers of inflammation as measured by circulating hs-CRP will be obtained at the beginning of each cycle.

Adverse events data will be summarized using tables and descriptive statistics.

The change in SPPB from baseline to 12 months will be measured as a continuous outcome. A clinically relevant change is a change in total score of 1, with a standard deviation at baseline of 1.5⁴².

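### Randomization is stratified by metastasis, but the log-rank tests for PSA and radiographic progression name no strata

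*Combined protocol and SAP*

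**What the plan says.** Section 4.1 sets the allocation: "Fifty-six patients will be 1:1 randomized to one of two treatment arms with metastasis as a stratification factor". That is the only mention of stratification in the document. Section 6.2 says only "Randomization will occur using the GraphPad QuickCalcs randomization service", and section 9.3 gives a 1:1 ratio administered by a central project manager. Neither repeats the stratum.

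Section 10.1.1 defines time to PSA progression and time to radiographic progression and compares both between arms: "Log rank test will be used to compare the distributions of above variables between the group treated with enzalutamide". No stratum or covariate is named there or anywhere else in section 10, and no reason is given for leaving the factor out.

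On prognosis, section 1.2 describes ADT as effective, with "survival results mainly impacted by disease state at initiation". On assessment times, section 7.2.1 says "Serum PSA will be obtained every 3 months", and section 7.2.2 says CT or MRI and "bone scan will occur at baseline, 6 months, and 12 months".

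**The concern.** A factor is normally chosen for stratified randomization because it is expected to predict outcome. Balancing on it removes part of the chance difference between arms, but the variance of an unstratified log-rank test still counts that part. The test therefore rejects too rarely under the null and has less power under the alternative. The benefit gained at randomization is given up at analysis.

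The stake is sensitivity, not false claims. In a comparison of enzalutamide monotherapy with standard ADT, these two tests are the plan's between-arm comparison of cancer control. A needlessly conservative test makes a real difference in either direction harder to see. Leaving the strata unstated also allows the choice of test to be made after the data are seen.

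**Working it through.** **The plan's own figure.** The plan sizes nothing on the log-rank tests. Its only power statement (section 10.1: 80% power, actual alpha 0.054, 28 per arm, 7% versus 32%) concerns the primary chi-square test. Exact enumeration of the one-sided pooled test gives 80.8–81.1% power and alpha 0.0538, so that statement reproduces. It has no bearing on this point.

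**Inputs from the documents.** N = 56, 1:1, stratified by metastasis (4.1); PSA every 3 months (7.2.1); imaging at 6 and 12 months (7.2.2); 12 months of treatment (4.1).

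**Assumptions, not in the documents.** Half the patients metastatic; exponential times from randomization; allocation balanced within stratum; two-sided 5%; treatment hazard ratio 0.5; metastatic hazard k = 1, 2, 3 or 4 times the non-metastatic hazard; overall control progression by 12 months of 20, 30, 50 or 70%.

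**Tests.** At visit *j*, with *d* events, *n* at risk and *n₁* at risk in arm 1: E = d·n₁/n and V = d·(n₁/n)(1 − n₁/n)(n − d)/(n − 1). The unstratified statistic is Σ(O − E)/√ΣV over all patients. The stratified one computes O − E and V within each metastasis stratum and adds them before dividing.

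**Setting the hazards.** Let q be the 12-month progression-free proportion in non-metastatic controls. Then ½q + ½qᵏ = 1 − (overall control progression). For k = 3 and 50%: q + q³ = 1, so q = 0.682 and q³ = 0.318. Control progression is 32% without and 68% with metastases. Under a treatment hazard ratio of 0.5 the progression-free proportions are √0.682 = 0.826 and √0.318 = 0.564. Expected events are 28 × 0.50 + 28 × (1 − (0.826 + 0.564)/2) = 14 + 8.5 = 22.5. Over the four progression rates the totals are about 9, 13, 22 and 33.

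**Simulation.** 60,000 runs per cell, event times rounded up to the next scheduled visit, censoring at 12 months.

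Size (treatment hazard ratio 1), over both schedules:

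| Metastatic hazard | Unstratified |
|---|---|
| 2× | 4.2–4.9% |
| 3× | 3.1–4.4% |
| 4× | 2.2–4.2% |

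The stratified test stays at 4.8–5.3%.

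Power gain from stratifying, in percentage points (PSA schedule / imaging schedule):

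| Metastatic hazard | 20% | 30% | 50% | 70% |
|---|---|---|---|---|
| 2× | +0.1/+0.1 | +0.7/+0.9 | +1.9/+1.5 | +3.0/+3.3 |
| 3× | +0.6/+0.5 | +2.0/+2.0 | +4.9/+4.5 | +8.9/+8.4 |
| 4× | +0.9/+0.9 | +3.2/+2.9 | +7.6/+7.2 | +14.5/+13.6 |

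Power itself at 3×, PSA schedule, unstratified versus stratified: 15.9 vs 16.5%, 20.5 vs 22.5%, 31.4 vs 36.3%, 41.1 vs 50.0%.

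**Sensitivity.**
- Metastasis not prognostic (1×): loss of at most 0.4 points.
- 10% control progression (about 4 events): no gain (−0.2 to 0.0).
- 11, 25 or 75% metastatic: −0.1 to +2.5 at 2×; +0.1 to +10.9 at 3–4×.
- Treatment hazard ratio 0.67: +0.1 to +2.4 at 2×; +0.5 to +9.4 at 3–4×.
- Continuous event times: gains within about 1.2 points of those above, for 20–70% progression.

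**Which columns are plausible.** Section 1.2 gives a median ADT response of 10.8 months in biochemically relapsed disease. If loss of response stands for progression and times are exponential, 1 − 0.5^(12/10.8) = 54% of such controls progress by 12 months. With half metastatic at 2× or 3× that hazard, overall progression is (54 + 79)/2 = 66% or (54 + 90)/2 = 72%. This points to the right-hand columns, but only loosely: other non-metastatic patients are eligible, and radiographic progression may be rarer.

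**The case against.** **It is not an error.** An unstratified log-rank test is valid, the endpoints are secondary, and no hypothesis or power is attached to them. This stands, and it limits the weight of the point.

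**Power is poor either way.** At 3× it moves from 15.9–41.1% to 16.5–50.0%, even at a hazard ratio of 0.5. With half the patients metastatic and that hazard ratio, gains above 5 points need 3× with 70% progression, or 4× with at least 50%. This also stands. It describes the size of the gain and is no reason to forgo it.

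**The prognostic premise is thin.** Section 1.2 speaks of survival, not of 12-month progression. True; the rest is inference from the choice of stratum, which is why the result is given as a range.

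**The conservatism depends on balance within strata.** Sections 6.2 and 9.3 describe no mechanism that secures it. With 28:28 allocation not balanced on metastasis (PSA schedule, 30–70% progression), unstratified size returns to 5.0–5.2%. Gains shrink to +0.2 to +2.4 points at 2×, +0.8 to +7.6 at 3× and +1.5 to +11.7 at 4×. The worst loss seen was about 0.9 points, when metastasis was not prognostic. That allocation would, however, depart from section 4.1.

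**PSA gains may be overstated.** Section 7.2.1 requires confirmation, and Table 1 schedules no PSA after Month 13 Day 1, so a first rise at 12 months has no scheduled confirming sample. Counting first rises only through month 9 gives −0.2 to +2.4 points at 2×, 0 to +6.4 at 3× and +0.2 to +11.1 at 4×. The gains are smaller, but at 50–70% progression and hazards of 2× or more they stay positive.

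**The PSA time origin is unsettled.** Section 10.1.1 measures from randomization, but also says that after a PSA decline "the PSA progression date is defined as the time from documented PSA nadir to an increase in PSA with confirmation". The PSA figures here hold for the randomization origin only. The two statements need reconciling separately.

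**Conclusion.** The mismatch is real: allocation is stratified by metastasis, and the two progression tests ignore the stratum without explanation. It cannot produce a false positive and touches no primary result. If allocation is balanced within strata as section 4.1 implies, the cost is a conservative test. In the main runs the power forgone is 0.1 to 3.3 points at a twofold metastatic hazard, 0.5 to 8.9 at threefold and 0.9 to 14.5 at fourfold, rising with the progression rate. It is negligible if few patients progress or metastasis is not prognostic. These figures rest on assumed progression rates, metastatic share and hazard ratios that the documents do not give. Against them stands a loss of at most about 0.4 points when the factor is irrelevant. The change should be made because it is nearly free, although both comparisons remain underpowered under every assumption tried.

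**What to change.** In section 10.1.1, state that time to PSA progression and time to radiographic progression are each compared by a log-rank test stratified by metastasis at screening, the randomization stratum of section 4.1. If the team prefers the unstratified test, it should say so in advance, give the reason, and report the stratified test as a sensitivity analysis.

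In sections 6.2 and 9.3, add a line on how the central manager implements the stratum, since the balance assumed here depends on it.

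The cost is wording only. Metastatic status is already known from the screening bone scan and CT (section 6.3.2: "CT scan and assessment of tumor burden, may use imaging study within 28 days of day 1"), so no patients, visits or data are added.

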- Verification of calcium/vitamin D administration

Month 7 Day 1+/- 5 days

- Physical examination
- Vital signs, including weight and waist circumference
- ECOG performance status

COMIRB/Protocol # 14-0909**Protocol Version:****4.27.2018 PI: [name]**

- Blood samples for CBC, Comprehensive metabolic panel (fasting), testosterone, PSA, N-telopeptide, bone specific alkaline phosphatase, lipid profile, estradiol, hs-CRP, 25-OH Vitamin D
- Optional tubes of blood for future biomarker testing
- FACT-P, SHIM completed
- CT scan and assessment of tumor burden +/- 5 days
- Bone scan +/- 5 days
- Short Physical Performance Battery
- Collection of concomitant medications
- Collection of adverse events
- Dosing of medication, or documentation of continued dosing
- Verification of calcium/vitamin D administration

Month 10 Day 1+- 5 days

- Physical examination
- Vital signs, including weight and waist circumference
- ECOG performance status
- Blood samples for CBC, Comprehensive metabolic panel (fasting), testosterone, PSA, N-telopeptide, bone specific alkaline phosphatase, lipid profile, estradiol, hs-CRP
- Optional tube of blood for future biomarker testing
- FACT-P, SHIM completed
- Short Physical Performance Battery
- Collection of concomitant medications
- Collection of adverse events
- Dosing of medication, or documentation of continued dosing
- Verification of calcium/vitamin D administration

Month 13 Day 1 or End of Treatment (+/- 5 days)

- Physical examination
- Vital signs, including weight and waist circumference
- ECOG performance status
- Blood samples for CBC, Comprehensive metabolic panel (fasting), testosterone, PSA, N-telopeptide, bone specific alkaline phosphatase, lipid profile, estradiol, hs-CRP, 25-OH Vitamin D
- Optional tubes of blood for future biomarker testing
- FACT-P, SHIM completed
- DXA scan (+/- 14 Days of Day 1 Dosing); note that there must be a 14 day separation of bone scan and a DXA scan
- CT scan and assessment of tumor burden +/- 5 days
- Bone scan +/- 5 days
- Short Physical Performance Battery
- Collection of concomitant medications
- Collection of adverse events

End of Study (EOS) safety visit

- Physical examination
- Vital signs, including weight and waist circumference

- ECOG performance status
- Blood samples for CBC, Comprehensive metabolic panel
- Collection of concomitant medications
- Collection of adverse events

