10. STATISTICAL AND QUANTITATIVE ANALYSES

10.1 Statistical Methods

We estimate a 7% (2 patients) and 32% (9 patients) incidence of metabolic syndrome for enzalutamide and ADT treated patients based on historic data ⁷. Historical cross-sectional data would suggest that almost 50% of patients on ADT will develop metabolic syndrome, however, the trial population proposed will be pre-selected. Twenty-eight (28) patients in each of the two groups will provide 80% power to detect the 25% difference using a one-sided chi-square test with a significance level of 0.05 (actual alpha=0.054).

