Mean, standard deviation, median, and range will be reported for each outcome at each time point, and the mean and standard deviation of the changes, will be calculated. One-group t-test will be used to estimate effect size of each outcome measure and test if the change is significant at 0.05 significance level. Pearson or Spearman correlation coefficients will be used to assess the association between continuous variables.

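### The 12-month SPPB change, and the month-12 tests of bone markers, bone density and body composition, are not defined for men who stop before month 12

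*Combined protocol and SAP*

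**What the plan says.** Section 10.1.1 fixes the SPPB endpoint at one time: "The change in SPPB from baseline to 12 months will be measured as a continuous outcome". The test comes at the end of that section: "One-group t-test will be used to estimate effect size of each outcome measure and test if the change is significant at 0.05 significance level". Bone turnover markers, and bone density with fat and fat-free mass, have within-arm paired t-tests at each time point. FACT-P and SHIM are assessed at each visit and, under section 7.4, used descriptively.

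Several rules stop a man before month 12. Section 7.2.1 requires treatment to stop at PSA progression. Section 4.4.2 bars further study treatment after progression. Section 7.2.2 goes further: "Patients will be removed from study if they have evidence of radiographic disease progression as defined below". Section 4.2 adds toxicity, non-compliance, intercurrent illness and withdrawal of consent.

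The last full assessment in section 6.3.2 is headed "Month 13 Day 1 or End of Treatment (+/- 5 days" and lists SPPB, FACT-P, SHIM, DXA, CT and bone markers. Section 7.8 asks instead for the End of Study procedures when study drug is discontinued, and the End of Study list in 6.3.2 contains none of these. Section 10.4 admits any treated man with a baseline and one post-baseline assessment. Section 10 gives no rule for missing values, no dropout rate and no statement of how early stopping is handled.

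**The concern.** A man who stops at month 5 belongs to the secondary endpoint population but has no true 12-month value. The plan leaves two ways to treat him, and they answer different questions.

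- **Only true month-12 values are used.** The estimate then describes men still under assessment at a year. If men who are declining leave sooner, it could understate decline. Values recorded at months 3, 6 and 9 play no part in the 12-month estimate.
- **The exit value is taken as month 12 because the visit label allows it.** Men with a few months of exposure are then averaged with men who had twelve.

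The choice could be made after the data are seen. If exit rates differ between arms, the descriptive comparison of enzalutamide with ADT could be distorted as well.

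**Working it through.** **1. The plan's own figure.** The only sample-size statement concerns metabolic syndrome: "Twenty-eight (28) patients in each of the two groups will provide 80% power to detect the 25% difference", with rates of 7% and 32%. Exact enumeration of the uncorrected one-sided chi-square test with 28 per arm gives power 81.1% and actual alpha 0.0538 at the average rate (0.07 + 0.32)/2 = 0.195. The stated 80% and 0.054 therefore reproduce. Nothing below depends on them. The plan has no power figure for SPPB.

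**2. Illustrative loss before the 12-month assessment.** The one relevant number is in section 1.2: "The median time of response for patients with biochemically relapsed disease treated with ADT is 10.8 months". Assume exponential response and, as an upper bound because the case mix is not given, an ADT arm made up entirely of such men. The share still responding at month t is S(t) = 0.5^(t/10.8).

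- t = 12: S = 0.463, so 53.7% have lost response. This overstates removal, because progression first found at the Month 13 Day 1 visit does not cancel that visit.
- t = 9 (Month 10 visit): S = 0.561, 43.9% lost, 28 × 0.561 = 15.7, about 16 left.
- t = 6, if a PSA rise seen at the Month 7 visit is confirmed only at the next 3-monthly sample: S = 0.680, 32.0% lost, 28 × 0.680 = 19.0, about 19 left.

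With Weibull shapes from 0.7 to 3 in place of the exponential, the ranges are 33% to 46% (t = 9) and 11% to 37% (t = 6).

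**3. Precision if only true month-12 values are used.** Section 10.1.1 calls 1 SPPB point clinically relevant and gives a baseline SD of 1.5. It gives no SD of change. I take 1.5, and 1.5 × √2 = 2.12 (zero correlation between the two values) as a wide case. One-group t-test, two-sided 0.05 (the plan does not state sidedness), noncentrality √n × 1/SD:

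| n | Power, SD 1.5 | Power, SD 2.12 |
|---|---|---|
| 28 | 92% | 67% |
| 19 | 79% | 49% |
| 16 | 70% | 42% |

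**4. Bias if exit values are taken as month 12.** Suppose a steady decline reaching −1.0 at month 12, and exit unrelated to SPPB at month 6 on average. With a share L leaving, the estimate is (1 − L)(−1.0) + L(−0.5).

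- L = 0.32: −0.68 − 0.16 = −0.84.
- L = 0.44: −0.56 − 0.22 = −0.78.

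No link between exit and outcome is needed, only change that accumulates.

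**5. Bias if only completers are used.** This does need a link. Simulation inputs, all assumed: individual slopes with mean −1.0 and SD 1.3 at 12 months, residual SD 0.7 per measurement, and logistic exit after months 3, 6 and 9 depending on the observed change.

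- No dependence: completer mean about −1.0, no bias.
- Log-odds of exit rising 0.75 per point of decline: about −0.68 at 32% lost and −0.55 at 44% lost.
- Log-odds rising 1.5 per point: about −0.51 and −0.33.

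A repeated-measures model on all visits, in simulations with 23% to 52% lost, gave −0.95 to −1.03. That is expected, since exit was generated from observed values, which is the model's own assumption.

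**The case against.** Three stronger readings are tempting, and the documents do not support them.

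A reader might infer that early leavers cannot be scored at all. Section 6.3.2 schedules the full battery at end of treatment, so an exit value can exist. What is missing is a rule for using it.

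A reader might also infer that about half the ADT arm will be gone by month 12. The 10.8 months is a response duration in biochemically relapsed men. Removal under section 7.2.1 needs a rise of at least 50% and 2 ng/mL above nadir, at least 12 weeks in and confirmed, or else radiographic progression. The trial also enrols metastatic men and men unsuited to local therapy, in unstated proportions.

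Finally, a reader might infer that every secondary change endpoint fails in this way, or that completer bias has been shown. Only SPPB is defined solely at 12 months. Bone markers, bone density and body composition are also tested earlier, FACT-P and SHIM are descriptive, and section 10.1.1 reports all outcomes at each time point. The protocol-defined progression triggers are PSA and imaging, not physical function, so a link between exit and SPPB is plausible but assumed.

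It can also be said that a mixed model is a preference for unpowered secondary outcomes in a 56-patient phase II trial. That bears on priority. It does not settle which value a man who stops at month 5 contributes.

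**Conclusion.** The point holds in a limited form. The 12-month SPPB change, and the month-12 tests of bone markers, bone density and body composition, have no definition for men who stop early. Both available readings can mislead: the completer reading if decliners leave early, the label reading whenever change accumulates over time. The direction of each follows under its stated condition. The sizes rest on assumptions that the documents do not supply: an ADT arm of biochemically relapsed men only, the shape of the response curve, an SD of change of 1.5 to 2.12, and the strength of any link between exit and SPPB. The 32% to 44% loss is an illustration for the ADT arm, not a forecast, and nothing in the documents supports a rate for enzalutamide. These are secondary endpoints and the primary analysis is untouched. The change is worth making because it is cheap and removes a choice that could otherwise be made after seeing the data.

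**What to change.** In section 10.1.1:

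- Estimate the 12-month change in SPPB with a repeated-measures mixed model using all scheduled values (baseline and months 3, 6, 9 and 12), with visit as a factor, and report the model-based 12-month change in each arm.
- Do the same for the other continuous outcomes with at least two scheduled post-baseline values: bone markers, DXA (months 3 and 12), CT measures (months 6 and 12), and FACT-P and SHIM if they are to be tested.
- Assign an early End of Treatment value to the nearest scheduled month by its actual date, never to month 12 by its label. State which value is used if that month already has one.
- Keep the observed-case summaries at each time point.

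Sections 6.3.2 and 7.8 must be reconciled on whether SPPB, quality of life, DXA and bone markers are collected when a man discontinues. The model can be fitted either way, but the data available at exit differ.

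Cost: analysis wording and a little more analysis work, using visits already scheduled. The downside is that the model relies on values being missing at random given those observed.
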